The ABBVIE REGIMEN has been studied with and without RBV in over 2,300 patients in Phase III trials across a variety of patient populations including those with compensated cirrhosis. Based on Phase III data, the ABBVIE REGIMEN, with or without RBV, was well tolerated with a low discontinuation rate. Adverse events (AEs) were typically mild, and many of the AEs and laboratory abnormalities reported were attributable to the presence of RBV. However, these AEs were much milder than observed when RBV was given in combination with interferon. Transient, asymptomatic serum alanine aminotransferase (ALT) elevations were observed at a low rate, were not associated with hepatic dysfunction and generally resolved with ongoing treatment. A disproportionate number of the cases were in women on concurrent ethinyl estradiol-containing therapy (i.e., contraceptives or hormone replacement) and discontinuation of the hormonal therapy with continuation or brief interruption of the ABBVIE REGIMEN led to resolution in serum ALT elevation. Transient elevations in serum bilirubin (predominantly indirect) were observed in subjects receiving the ABBVIE REGIMEN with RBV, related to the inhibition of the bilirubin transporters, organic anion-transporting polypeptides (OATPs) 1B1/1B3, by paritaprevir and RBV-induced hemolysis. Bilirubin elevations occurred after initiation of treatment, peaked by study Week 1, and generally resolved with ongoing therapy. Bilirubin elevations were not associated with aminotransferase elevations. The frequency of indirect bilirubin elevations was lower among subjects who did not receive RBV.

Response of CHC genotype 4 was assessed in the phase II study PEARL-I in which 86 treatment-naïve patients were randomized to the 2 DAA combination of paritaprevir/r – ombitasvir with vs. without RBV for 12 weeks. The SVR was 100% with RBV vs. 91% without RBV [61]. No serious SAEs or AEs leading to discontinuation were reported.

These results from pivotal studies are encouraging and the new interferon-free regimens might provide physicians with the armamentarium to cure the vast majority of patients

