#### **9.4.1.5 Concomitant Medication**

**Concomitant medication** - the following will be documented:

- Concomitant medication used from the time when the decision is made to initiate treatment with the ABBVIE REGIMEN until after the last dose

It should be verified by the treating physician that concomitant medication can be safely administered with the ABBVIE REGIMEN (including ritonavir) and RBV. Some medications may be contra-indicated, some may require dose adjustments due to potential for drug-drug interactions (DDIs). The investigator or qualified designee should review the concomitant medication(s) labels and screen concomitant medications at each visit for potential DDIs.

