4.2.8 Analyses of Safety

All safety variables will be summarized for patients in the SP using descriptive statistical methods stratified by treatment regimen and cirrhosis status and overall.

An overview of tables for the individual values is given in Table 12.

The layouts of the tables mentioned above are provided in Part II of the SAP (Table Shells).

4.2.8.1 *Exposure to Study Medication*

One table will show the frequencies for early discontinuation and exceedance of Abbvie Regimen or Ribavirin and the corresponding reasons for SP by treatment regimen and cirrhosis status. The Abbvie Regimen is considered to have been prematurely discontinued if actual duration is shortened for more than 7 days. The duration for taking Abbvie regimen is considered to have been exceeded if the actual duration is prolonged for more than 7 days. Furthermore, summary statistics will be generated for the duration of ABBVIE regimen taken and the duration of ribavirin taken, i.e. n, mean, median, standard deviation [SD], minimum, maximum.

Unintended medication errors, i.e. patient missed taking Paritaprevir/r-Ombitasvir or Dasabuvir for at least 7 days in a row, will be displayed by medication for the entire treatment period.

4.2.8.2 *Co-medication*

Treatments, surgical and medical procedures will be coded by AbbVie assigning appropriate preferred and class terms. Frequencies will be displayed for SP by treatment regimen and cirrhosis status.

In one table, the co-medication (preferred term) will be grouped by class. Only co-medication received during treatment specified by ABBVIE regimen will be displayed (Treatment profiles: A1, A2, C1 Drug B, C2 Drug B, C3 Drug B, D).

In another table the co-medication (preferred term) will be grouped by profile. All treatment profiles will be considered, i.e.:

- A1: Continued (A1)
- A2: Permanently discontinued during CHC treatment (A2)
- A3: Permanently discontinued prior to CHC treatment (A3)
- B: Discontinued prior to CHC treatment and reintroduced post-treatment (B)
- C1 Drug A: Permanently replaced at start of CHC treatment (C1A)
- C1 Drug B: Substitute at start of CHC treatment and discontinued during CHC treatment (C1B)
- C2 Drug A: Permanently replaced at start of CHC treatment (C2A)
- C2 Drug B: Substitute at start of CHC treatment and continued (C2B)
- C3 Drug A: Replaced during CHC treatment (C3A)
- C3 Drug B: Substitute during CHC treatment (C3B)
- D: Introduced during CHC treatment (D)

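### The SAP's by-class table of on-treatment co-medication omits profile C3 Drug A, although those drugs were taken with the regimen until they were replaced

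*SAP*

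**What the plan says.** SAP 4.2.8.2 describes four co-medication summaries for the safety population, apart from a glossary. The first groups preferred terms by class (output tcom_<c>_tc_sp in SAP Table 12). Its scope is stated in words: "Only co-medication received during treatment specified by ABBVIE regimen will be displayed". The scope is then put into operation as a list of codes, so that such co-medication "will be displayed (Treatment profiles: A1, A2, C1 Drug B, C2 Drug B, C3 Drug B, D").

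The definitions of the codes follow in the same section. Two matter most here: "C3 Drug A: Replaced during CHC treatment (C3A") and "A2: Permanently discontinued during CHC treatment (A2"). For contrast, the first drug of a C1 pair is defined by a switch at the outset: "C1 Drug A: Permanently replaced at start of CHC treatment (C1A"). C2 Drug A is defined in the same way as C1 Drug A.

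The other three summaries (by profile, by medication of special interest, and by associated treated condition) use all profiles. The SAP gives no reason for leaving C3 Drug A out of the first.

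**The concern.** The scope sentence and the code list are meant to say the same thing, and they do not. A drug replaced partway through therapy was received during therapy. Whether a substitute followed has no bearing on that, yet it is the only difference between C3 Drug A, which is left out, and A2, which is kept. The table would show the substitute (C3 Drug B) but not the drug it replaced.

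What is at stake is the accuracy of a descriptive exposure table. Co-medication is an objective in SAP section 2 and a secondary variable in SAP 4.1.2, and Protocol 9.4.1.5 asks sites to "screen concomitant medications at each visit for potential DDIs". A reader who wants to know how many patients took a given drug or class together with the regimen would go to this table. Its title in SAP Table 12 gives no hint that one on-treatment group is missing.

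**Working it through.** No arithmetic beyond counting applies. The check sets each profile definition in SAP 4.2.8.2 against two questions: by definition, was the drug taken during CHC treatment, and is the code in the list for the by-class table?

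| Profile | Meaning (paraphrased) | Taken during treatment? | In the list? |
|---|---|---|---|
| A1 | continued | yes | yes |
| A2 | stopped for good during treatment | yes, until stopped | yes |
| A3 | stopped for good before treatment | no | no |
| B | stopped before, resumed after | no | no |
| C1 Drug A | replaced at the start | no | no |
| C1 Drug B | substitute from the start, stopped during | yes, until stopped | yes |
| C2 Drug A | replaced at the start | no | no |
| C2 Drug B | substitute from the start, continued | yes | yes |
| **C3 Drug A** | **replaced during treatment** | **yes, until replaced** | **no** |
| C3 Drug B | substitute introduced during treatment | yes | yes |
| D | newly introduced during treatment | yes | yes |

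- Named profiles: 11, of which 7 are on-treatment and 4 are not (7 + 4 = 11).
- On-treatment profiles listed: 6 of 7. Missing: 7 − 6 = 1, C3 Drug A.
- Off-treatment profiles listed by mistake: 0 of 4.
- A twelfth category, for drugs with no profile recorded, is also outside the list, but its timing is unknown, so it cannot be classified.

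The list is therefore right for 10 of the 11 named profiles. Ending partway through therapy cannot be the ground for exclusion, because A2 and C1 Drug B also end partway and both are listed.

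Effect on the counts for one C3 pair in one patient:

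- **Substitute in the same class.** The patient still counts in the class through C3 Drug B. The preferred term of the first drug is lost.
- **Substitute in another class.** The preferred term of the first drug is lost, and so is the patient's count in the first drug's class, unless the patient took another listed drug of that class.
- **Substitute coded to the same preferred term.** Nothing is lost.

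The documents give no expected or observed number of C3 pairs, so these effects cannot be turned into a rate.

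**The case against.** The best case on the other side accepts the inconsistency and argues that little follows from it.

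**C3 Drug A is reported elsewhere.** This stands. The by-profile table shows it by preferred term for the same population, treatment regimens and cirrhosis strata. The treated-conditions table includes it, and so does the special-interest table where the drug falls in a selected group. The data are not lost from the report. These tables are only a partial substitute, however. The by-profile table is not organised by class, and its counts cannot simply be added because one patient may appear under several profiles. The special-interest table covers selected medications only. The treated-conditions table mixes in drugs stopped before treatment.

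**The tables would differ anyway.** This also stands. The by-class and by-profile tables have different scopes, so a difference between them is not in itself evidence of error. The point rests on the by-class table contradicting its own scope.

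**Stronger readings.** A reader might infer that drugs switched mid-treatment are the group most likely to involve interactions. The documents do not rank profiles by interaction risk or tie a replacement to a cause, and a drug stopped without a substitute could reflect an interaction equally well. A reader might also infer that the hormone-related ALT elevations in Protocol 7.1 would drop out of the table. That passage reports that "discontinuation of the hormonal therapy with continuation or brief interruption of the ABBVIE REGIMEN led to resolution in serum ALT elevation". It describes stopping, not replacing. A permanent stop during treatment is A2, which is counted. Finally, saying that all C3 Drug A exposure is missing from the table only restates the omission and does not measure its effect.

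**Conclusion.** The point holds as an internal inconsistency in SAP 4.2.8.2: the code list does not deliver the scope that the sentence before it sets. As written, tcom_<c>_tc_sp undercounts on-treatment co-medication by preferred term, and by class when the substitute is in a different class. The size is unknown and could be small.

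The consequence is confined to one descriptive safety table. SVR12, its confidence intervals, the regression models, the adverse event tables and the analysis populations are unaffected.

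Two assumptions underlie this. CHC treatment in the profile definitions is taken to mean the studied regimen, which is how the SAP itself must read it to include A2. The table shells in Part II of the SAP are also assumed to follow the list in the text; they are not among the documents reviewed.

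**What to change.** In SAP 4.2.8.2, change the profile list for the by-class table to A1, A2, C1 Drug B, C2 Drug B, C3 Drug A, C3 Drug B, D. If the omission was deliberate, state the reason in the SAP and in a footnote to the table. It would help to say in the same edit how drugs with no recorded profile are handled, since they too fall outside the filter.

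The cost is one code added to one filter, with no new data collection. The interim outputs listed in SAP 4.2.9 include no co-medication table, so none of those needs revision. The SAP is dated 22 November 2016 and the protocol plans data collection to August 2018, so on the planned timeline the change precedes the final analysis.

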4.2.8.3 Adverse Events

All tolerability variables will be summarized using descriptive statistical methods for the SP stratified by treatment regimen and cirrhosis status and overall.

AEs will be coded using MedDRA. A glossary will show the verbatim terms and the corresponding coded terms used (see Table 12).

The number and percentage of patients with treatment-emergent AEs (i.e. any reported event that begins or worsens in severity after initiation of study drug through 30 days post-study drug dosing including those who are related to the study drug independent of the occurrence and those where the date of onset is missing) will be tabulated by primary MedDRA SOC and PT.

Corresponding summary tables will be provided for all serious treatment-emergent AEs and additional for all non-serious treatment-emergent AEs. In the table of non-serious AEs (that must exclude any SAE) only preferred terms that occurred at a frequency of $\geq 5\%$ in any treatment group will be displayed (no SOCs will be displayed).

The tabulation of the number of patients with treatment-emergent AEs by severity (AEs by severity [mild, moderate, severe], AEs leading to death, AEs leading to hospitalization) and relationship to study drug will also be provided (ABBVIE Regimen, ribavirin, medication error - paritaprevir/r-ombitasvir, medication error – dasabuvir, ABBVIE Regimen withdrawn, ribavirin withdrawn).

Patients reporting more than one AE for a given MedDRA PT will be counted only once for that term using the most severe incident for the severity summary table and the most related for the relationship summary table. Patients reporting more than one type of event within a SOC will be counted only once for that SOC.

The frequency of pregnancies will be displayed as well.

4.2.8.4 Laboratory Data

All reported clinical laboratory test results will be assigned to one of the time points using the time windows specified in the Table 4. All will be performed for the SP by treatment regimen and cirrhosis status.

Changes from baseline to each post-baseline visit will be summarized descriptively (N, mean, SD, median, minimum, maximum). A summary table will show laboratory hematology. In another table information about clinical chemistry

In a further table CD4 and HIV-RNA are displayed for patients with HIV only by visit. A further table will show the viral resistance.

Instead of the shift tables mentioned in the study protocol, the number and percentage of subjects with post-baseline values until EoT meeting the specified criteria for Potentially Clinically Significant (PCS) laboratory values (defined in Table 10) will be summarized. A post-baseline value must be more extreme than the baseline value to be considered a PCS finding.

Table 10 Criteria for PCS laboratory values

Laboratory data	Very Low	Very High
Laboratory hematology		
Hemoglobin [g/L]	<80	
Platelets [10^9 /L]	<50	
Laboratory clinical chemistry		
ALT		>5 x ULN and >= 2 x baseline
AST		>5 x ULN and >= 2 x baseline
Creatinine [$\mu\text{mol}/\text{L}$]		>132.605
Creatinine clearance [mL/min]***	<50	

*** estimated by Cockcroft-Gault-Formula (see above)

Additionally, for hemoglobin and creatinine clearance, the number and percentage of subjects with a maximum Common Terminology Criteria for Adverse Events (CTCAE) Grade of 0, 1, 2, 3, or 4 (see definitions in Table 11) at any post-baseline visit (regardless of the baseline value) through the end of treatment (i.e., Final Treatment Value) will be summarized. For the liver function tests (LFTs) of ALT and AST, the number and percentage of subjects in with a maximum CTCAE Grade of 0, 1, 2, 3, or 4 (see definitions in Table 11) at any post-nadir visit through the end of treatment (i.e., Final Treatment Value) will be summarized. Note, for these analyses, the nadir is used for reference (including baseline).

Table 11 Definition of CTCAE Grades 0-4

Laboratory data	Grade 0	Grade 1	Grade 2	Grade 3	Grade 4
ALT	<=ULN	>ULN – 3 x ULN	> 3 – 5 x ULN	> 5 – 20 x ULN	> 20 x ULN
AST	<=ULN	>ULN – 3 x ULN	> 3 – 5 x ULN	> 5 – 20 x ULN	> 20 x ULN
Hemoglobin Decreased [g/L]	>=130	<130 – 100	< 100 - 80	< 80 - 65	< 65
Creatinine Clearance [mL/min]	>= 75	< 75 - 60	< 60 - 30	< 30 – 15	< 15

Table 12 Overview of Outputs for Safety Variables

Output Title	Output Short Name	Analysis Population
Exposure to Study Medication by Treatment Regimen and Cirrhosis Status - SP - <country>	tesm_<c>_tc_sp	Safety population
Unintended Medication Error /Pregnancy by Treatment Regimen and Cirrhosis Status -- SP - <country>	tum_<c>_tc_sp	Safety population
Treatment-emergent AEs by Treatment Regimen and Cirrhosis Status - SP - <country>	tae_<c>_tc_sp	Safety population
Serious Treatment-emergent AEs by Treatment Regimen and Cirrhosis Status - SP - <country>	tsae_<c>_tc_sp	Safety population
Non-Serious Treatment-emergent AEs by Treatment Regimen and Cirrhosis Status - SP - <country>	tnsae_<c>_tc_sp	Safety population
Treatment-emergent AEs by Severity by Treatment Regimen and Cirrhosis Status - SP - <country>	taes_<c>_tc_sp	Safety population
Treatment-emergent AEs Leading to Death by Treatment Regimen and Cirrhosis Status - SP - <country>	taed_<c>_tc_sp	Safety population
Treatment-emergent AEs Leading to Hospitalization by Treatment Regimen and Cirrhosis Status - SP - <country>	taeh_<c>_tc_sp	Safety population
Treatment-emergent AEs Possibly Related to ABBVIE Regimen by Treatment Regimen and Cirrhosis Status - SP - <country>	taera_<c>_tc_sp	Safety population
Treatment-emergent AEs Possibly Related to Ribavirin in Patients taking RBV by Treatment Regimen and Cirrhosis Status - SP - <country>	taerr_<c>_tc_sp_RB V	Safety population: patients taking RBV
Treatment-emergent AEs Caused by Medication Error - Paritaprevir/r-Ombitasvir - by Treatment Regimen and Cirrhosis Status - SP - <country>	taempo_<c>_tc_sp	Safety population
Treatment-emergent AEs Caused by Medication Error - Dasabuvir - in Patients taking 3DAA by Treatment Regimen and Cirrhosis Status - SP - <country>	taemd_<c>_tc_sp_3d aa	Safety population: patients taking 3DAA
Treatment-emergent AEs Leading to Withdrawal of ABBVIE Regimen by Treatment Regimen and Cirrhosis Status - SP - <country>	taewa_<c>_tc_sp	Safety population
Treatment-emergent AEs Leading to Withdrawal of Ribavirin in Patients taking RBV by Treatment Regimen and Cirrhosis Status - SP - <country>	taewr_<c>_tc_sp_RB V	Safety population: patients taking RBV
Listing of SAEs - SP - <country>	lsae_<c>_sp	Safety population
Glossary for AEs - <country>	tgae_<c>	-
Co-medication by Treatment Regimen and Cirrhosis Status - SP - <country>	tcom_<c>_tc_sp	Safety population
Co-medication by Profile and by Treatment Regimen and Cirrhosis Status - SP - <country>	tcomp_<c>_tc_sp	Safety population
Associated Treated Condition by Treatment Regimen and Cirrhosis Status - SP - <country>	tatc_<c>_tc_sp	Safety population
Associated Treatment Profiles by Medication of Special Interest and by Treatment Regimen and Cirrhosis Status - SP - <country>	tatp_<c>_mtc_sp	Safety population

Glossary for Co-medication - <country>	tgcom_<c>	-
Laboratory Hematology by Treatment Regimen and Cirrhosis Status - SP - <country>	tlh_<c>_tc_sp	Safety population
Laboratory Clinical Chemistry by Treatment Regimen and Cirrhosis Status - SP - <country>	tlc_<c>_tc_sp	Safety population
CD4 and HIV RNA in Patients With HIV by Treatment Regimen and Cirrhosis Status - SP - <country>	tlch_<c>_tc_sp_hiv	Safety population
Potentially Clinically Significant Laboratory Values by Treatment Regimen and Cirrhosis Status - SP - <country>	tpcs_<c>_tc_sp	Safety population
Worst Laboratory Values by Treatment Regimen and Cirrhosis Status - SP - <country>	twlv_<c>_tc_sp	Safety population
Viral Resistance by Treatment Regimen and Cirrhosis Status - SP - <country>	tlvr_<c>_tc_sp	Safety population

The layouts of the tables mentioned above are provided in Part II of the SAP (Table Shells).

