#### **9.4.1.2 During Treatment Documentation**

Follow-up visits are scheduled by the physician per routine clinical practice. Likewise treatment, procedures and diagnostic methods will follow physicians' routine clinical practice.

The following will be documented:

- Laboratory data

Key clinical chemistry	Remarks
▪ ALT	including ULN
▪ AST	including ULN,
▪ γ-GT	APRI and FIB-4 will be calculated
▪ Total bilirubin	
▪ Creatinine	creatinine clearance will be calculated
Key hematology	
▪ Hb	
▪ Platelets	
Virology	
▪ HCV RNA	quantitative/ qualitative HCV RNA PCR test, see 9.4.1.4
HIV-infected patients only	
▪ CD 4 count	most recent assessment
▪ HIV RNA	in copies/mL

- Concomitant medication, see 9.4.1.5
- Adherence to ABBVIE REGIMEN ± RBV (ABBVIE REGIMEN - % of target dose taken and RBV Y/N)  
*A period of 7 days in a row of missed intake of the **ABBVIE Regimen** during the time between documented first dose and last dose will issue a medication error report.*
- Tolerability (sAEs and AEs, see 11.5) and pregnancies (see 11.6)
- Data on portal hypertension (for patients with cirrhosis only): HVPG or clinical assessments (e.g. splenomegaly, presence of esophageal varices, surrogate lab markers, CT, MRI) (EoT only)
- Viral resistance (blood for viral sequencing) (EoT only)
- PSP satisfaction and utilization questionnaires, PAM-13 and BMQ: only at EOT/premature discontinuation

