**Table 4 - Analysis Time Windows**

Phase	Time point	Time Window
Pre-Treatment	Baseline	Last value prior to start of study treatment (i.e. $\leq$ study day 1)
Treatment Weeks		Study day during treatment period (Study day 1 = first treatment day)
	4 (day 29)	15 - 42
	8 (day 57)	43 - 70
	12 (day 85)	71 - 98
	16 (day 113)	99 - 126
EoT	Actual EoT	Study day of last dose (28 days prior to EoT - 14 days post EoT)
Post Treatment	4 weeks (day 29 post EoT)	15 – 56 post EoT
	12 weeks (day 85 post EoT)	57 – 112 post EoT
	24 weeks (day 169 post EoT)	141 – 196 post EoT

Mean changes from baseline to each post-baseline visit will be summarized descriptively.

Laboratory data values collected during the treatment period will be categorized as low, normal, or high based on reference ranges used in this study. The number and percent of patients who experience post-baseline shifts during treatment in clinical laboratory values from low/normal to high and high/normal to low based on the reference range will be summarized.

Additional details of the analyses of clinical laboratory data will be specified in the SAP.

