EoT	Actual EoT	Study day of last dose# (28 days prior to last dose - 7 days post last dose)
Post Treatment	12 weeks (SVR 12 window)	\geq 70-126 days post last dose
	24 weeks (SVR24 window)	127-210 days post last dose

[^]values must also be \leq 7 days post last dose

\geq study day 2

*RVR = rapid virological response

All reported safety laboratory test results will be assigned to one of the time points using the time windows specified in the table below.

Table 4 - Analysis Time Windows for Safety Laboratory Data

Phase	Time point	Time Window
Pre-Treatment	Baseline	Last value prior to start of study treatment (i.e. \leq study day 1)
Treatment Weeks	4 (day 29)	Study day during treatment period (Study day 1 = first treatment day)
	8 (day 57)	15 – 42 [^]
	12 (day 85)	43 – 70 [^]
	16 (day 113)	71 – 98 [^]
EoT	Actual EoT	Study day of last dose# (28 days prior to last dose - 7 days post last dose)
Post Treatment	4 weeks (28 days post last dose)	8– 56 post last dose
	12 weeks (84 days post last dose)	57 – 126 days post last dose
	24 weeks (168 days post last dose)	127 – 252 days post last dose

[^]values must also be \leq 7 days post last dose

\geq study day 2

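### SAP Tables 10 and 11 omit total bilirubin and the first on-treatment laboratory window opens at day 15, so a Week 1 bilirubin rise gets no laboratory summary in patients treated to day 43 or later

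*SAP*

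**What the plan says.** Protocol Section 7.1 describes one laboratory effect with a stated early time course: "Transient elevations in serum bilirubin (predominantly indirect) were observed in subjects receiving the ABBVIE REGIMEN with RBV", and then "Bilirubin elevations occurred after initiation of treatment, peaked by study Week 1, and generally resolved with ongoing therapy". Protocol Sections 9.4.1.1 to 9.4.1.3 list total bilirubin among the chemistry values to be documented at inclusion, during treatment and after treatment, where routine practice provides them.

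Protocol Section 9.7.4 planned a categorical summary: "Laboratory data values collected during the treatment period will be categorized as low, normal, or high based on reference ranges used in this study". It then asks for a count: "The number and percent of patients who experience post-baseline shifts during treatment in clinical laboratory values from low/normal to high", and likewise for shifts downwards. It names no analytes and does not tie these shifts to visit windows.

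SAP Section 4.2.8.4 replaces this: "Instead of the shift tables mentioned in the study protocol, the number and percentage of subjects with post-baseline values until EoT" meeting the criteria of Table 10 are counted, provided that the value is more extreme than baseline. Table 11 adds toxicity grades. By-visit changes from baseline stay, with minimum and maximum. On timing, SAP Section 4.2.2 says: "All reported safety laboratory test results will be assigned to one of the time points using the time windows specified" in SAP Table 4, and Section 4.2.8.4 repeats this rule.

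**The concern.** The SAP took away the one laboratory summary that could have counted an early bilirubin rise whenever it occurred during treatment. The analyte lists that took its place leave bilirubin out, and no reason is given. The by-visit changes that remain begin after the time at which the protocol expects the peak.

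Describing tolerability is a secondary objective in SAP Section 2, and the safety tables are split by ribavirin use and cirrhosis status. That is the split in which a reader would look for this effect, since the protocol reports it in patients taking ribavirin and at lower frequency without it. The stake is a gap in a descriptive safety output. No effectiveness estimate depends on it.

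**Working it through.** The plan gives no figure to reproduce here. The check has two parts.

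**1. Which analytes are covered**

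| Analyte documented on treatment (Protocol 9.4.1.2) | SAP Table 10 | SAP Table 11 |
|---|---|---|
| ALT | yes | yes |
| AST | yes | yes |
| Haemoglobin | yes | yes |
| Platelets | yes | no |
| Creatinine | yes | no |
| Creatinine clearance (derived) | yes | yes |
| Total bilirubin | no | no |
| γ-GT | no | no |

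Table 10 has 6 rows and Table 11 has 4. Bilirubin and γ-GT are in neither. The protocol attaches no early effect to γ-GT, so the point is confined to bilirubin.

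**2. Which study days fall in a window**

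Inputs from SAP Table 4: baseline is day 1 or earlier; the first on-treatment window (week 4) is days 15 to 42; the EoT window runs from 28 days before to 7 days after the last dose and not before day 2; the 4-week post-treatment window is 8 to 56 days after the last dose. The rows of SAP Table 4 look displaced in the available text. I take days 15 to 42 as week 4, as in SAP Table 3 and protocol Table 4. Under either reading no scheduled on-treatment window opens before day 15.

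The days between baseline and the first on-treatment window are 2 to 14, that is 14 − 2 + 1 = 13 days.

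Let L be the study day of the last dose. The EoT window is max(2, L − 28) to L + 7.

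- It reaches day 14 only if L − 28 ≤ 14, so L ≤ 42.
- It reaches day 8 only if L − 28 ≤ 8, so L ≤ 36.
- It reaches back to day 2 only if L − 28 ≤ 2, so L ≤ 30. For L of 6 or less the last few of the 13 days fall after L + 7 and are picked up by the post-treatment window, so all 13 are covered whenever L ≤ 30.

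| Last dose L | EoT window | Days 2–14 in no window |
|---|---|---|
| 30 | 2–37 | none |
| 35 | 7–42 | 2–6 |
| 42 | 14–49 | 2–13 |
| 43 | 15–50 | all 13 |
| 84 (12 weeks) | 56–91 | all 13 |
| 168 (24 weeks) | 140–175 | all 13 |

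Protocol Table 4, whose EoT window ends 14 days after the last dose, gives the same cut-offs of 30, 36 and 42. The window gap is therefore inherited. What the SAP changed is the loss of the shift analysis, which had no window limit.

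**Consequence.** The SAP's rule that every laboratory result goes to a Table 4 time point cannot be met for a day 2 to 14 value when L is 43 or more. Table 10 is worded by values after baseline up to EoT, not by visit, so a bilirubin row there could count such a value without a new window.

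**The case against.** Several stronger readings are tempting, and the documents do not support them.

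- A reader might infer that bilirubin is reported nowhere. The SAP keeps by-visit changes in a clinical chemistry table, which should carry bilirubin from week 4 on. The analytes are set in the Part II table shells, which are not among the documents reviewed. Protocol Section 11.1 counts an abnormal laboratory finding as a possible adverse event, so a rise reported as one would appear in the tables of SAP Section 4.2.8.3. That route depends on the investigator choosing to report a transient change.
- A reader might infer that the report would look benign because values are discarded. The documents do not show how many Week 1 values exist. Testing follows routine practice, and a 12-week course has few documented contacts on treatment. The 13 uncovered days out of 84 are a share of the calendar, not of the data. Since the SAP also says that all results are assigned to a window, discarding is one reading of a contradiction, not a stated rule.
- A reader might infer that the SAP created the window gap, or that it holds for everyone. It stands in protocol Table 4 too, and it closes partly or wholly for patients who stop by day 42.
- A reader might object that Table 11 grades haemoglobin and creatinine clearance "at any post-baseline visit (regardless of the baseline value") and so mixes earlier abnormality with treatment effect. The SAP says this openly, Table 10 requires worsening from baseline for both, and changes from baseline are tabulated. A cross-table by baseline grade would be a preference.

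It is also fair that the protocol names no analytes for its shifts and lists an upper limit of normal only for ALT and AST, so a bilirubin shift was implied rather than fully specified. The SAP discloses the replacement, and the protocol describes the rises as transient and not associated with aminotransferase elevations.

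These arguments limit the size of the point. None of them puts a threshold-based bilirubin summary back into the SAP text.

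**Conclusion.** The point holds in a limited form. Total bilirubin is absent from both tables that took over from the shift analysis, and a Week 1 value enters no laboratory summary for a patient whose last dose is on day 43 or later. That covers every patient who completes a planned course. By-visit changes from day 15 and any adverse event reports remain. Separately, the rule that all results are assigned to a SAP Table 4 time point contradicts the windows in that table and needs reconciling.

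This rests on three assumptions: that the week 4 window is days 15 to 42, that the Part II shells add no bilirubin row or early window, and that the protocol's general reference to laboratory values included bilirubin. The practical yield depends on how many early values sites recorded, which may be few. It is a cheap improvement to a descriptive safety output and leaves the SVR12 analysis untouched.

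**What to change.** 1. Add a total bilirubin row to SAP Table 10: the worst value after baseline up to EoT that is more extreme than baseline, shown in the existing safety population groups with and without ribavirin. Use a multiple of the upper limit of normal if that limit is available for bilirubin. Otherwise use fixed reporting cut-offs such as those in protocol Annex 5 (34.2 and 51.3 µmol/L), as Table 10 already does for creatinine.
2. In SAP Table 4, either add an early on-treatment window for days 2 to 14, or state that values from those days enter only the worst-value tables. Reword the rule on assigning all results to match.

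The cost is one table row and one sentence or window, using whatever bilirubin values sites have entered. The drawbacks are that fixed cut-offs ignore differences between local laboratories, and that those in Annex 5 were set to score severity of cirrhosis. They would serve here only as reporting thresholds.
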